9.4.6.1 Part 1 (Dose Escalation): Recommended Phase 2 Dose

The primary endpoint for Part 1 (dose escalation) is the number of DLTs, which will be used to estimate the MTD and select the RP2D. This will be determined by the dose level at which no more than 1 patient out of 6 patients experiences a DLT during Cycle 1.

For assessment of DLTs, toxicities will be coded using the Medical Dictionary for Regulatory Activities (MedDRA) v22.0 or higher and graded according to NCI-CTCAE v5.0. See Section 7.1.2.2 for details on DLT criteria.

The number of DLTs experienced by a patient will be summarized by DLT type for each dose cohort and DLT events will be listed by patient. The listing will include the description, severity and relationship of the events to study drug.

9.4.6.2 Part 2 (Dose Expansion)

The primary endpoints for Part 2 (dose expansion) are:

- Arm 1 (mCRPC): The proportion of patients who achieve ≥ 30% reduction in PSA from baseline at the end of Cycles 3 and 6.
- Arm 2 (BC and NSCLC): Disease control rate assessed by determining the percentage of patients with CR, PR, plus SD.

For patients with mCRPC, plasma levels of PSA will be collected on Day 1 of Cycles 1 to 5, every second cycle thereafter (i.e., Cycles 7, 9, 11 etc.), at the EOT/ED Visit and at the 6-, 9- and 12 month Follow-up Visits for all patients including those that discontinued for any reason other than disease progression. The number and proportions of patients with $a \ge 30\%$ reduction in PSA levels from baseline to the end of Cycles 3 and 6 (primary endpoint) and change from baseline at any time point (secondary endpoint) will be presented for Treatment Arm 1 along with the corresponding exact 95% CI (Clopper-Pearson).

The effect of NOX66 on DCR will be assessed based on the percentage of patients with the best overall response of CR or PR at any time plus SD from first dose administration until disease progression, death due to any cause or the start of new anticancer therapy, respectively. RECIST v1.1 criteria will be applied to assess CR, PR and SD. Disease control rate will be presented for Treatment Arm 2 along with the corresponding exact 95% CI (Clopper-Pearson). Tumor imaging and disease response assessments will be performed for up to 12 months after the last dose of study drug until disease progression, withdrawal of consent, initiation of new anticancer therapy, the patient is lost to follow-up or death, whichever comes first.

9.4.7 Secondary Endpoint(s)

9.4.7.1 Safety of NOX66 and Both Doses of EBRT

Safety profiles will be summarized by NOX66 dose cohort and separately by EBRT dose cohort (Part 1) or treatment arm and separately by EBRT dose cohort (Part 2) and will be based on the Safety Analysis Set.

Adverse events will be coded using the MedDRA v22.0 or higher and will be graded according to the NCI-CTCAE v5.0. Treatment-emergent AEs are defined as those AEs that either start or

worsen in severity on or after the date of first administration of study drug and on or before 30 days after the last dose of study drug.

Treatment-emergent AEs will be summarized by severity grade and relationship to study drug. Serious AEs, serious TEAEs and TEAEs leading to discontinuation of study drug or to death will be presented.

Changes in clinical laboratory values, vital signs, ECGs and physical examinations will be summarized over time.

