4.1 Overall Design

This is a Phase 1b/Phase 2a, open-label, multicenter study to determine the safety, tolerability, RP2D, efficacy, pharmacokinetics (PK) and pharmacodynamic (PD) properties of idronoxil when rectally administered as a suppository (NOX66) to patients with any solid tumor (Part 1) and patients with mCRPC, BC and NSCLC (Part 2) who are eligible for low-dose EBRT for at least one symptomatic or minimally symptomatic lesion (for the prevention of symptoms). The study will be performed in approximately 14 sites in Australia, United States (US) and Europe. The study is divided into 2 parts: Part 1 (dose escalation) and Part 2 (dose expansion). The study design allows an exploration of different doses of NOX66 (800 mg, 1200 mg, 1600 mg and 2400 mg) with safety monitoring to ensure the safety of the patients. A Safety Steering Committee (SSC) will review available safety data after the first cycle (21 days) of each dose cohort of NOX66 in Part 1 to determine the maximum tolerated dose (MTD)/RP2D.

In Cycle 1, NOX66 will be administered for 14 days followed by a 7-day rest period on a 21-day cycle. From Cycle 2 onwards, NOX66 will be administered for 7 days followed by a 7-day rest period on a 14-day cycle. Patients will continue to receive NOX66 on a cyclical basis until

disease progression, unacceptable toxicity, withdrawal of consent, start of a new anticancer therapy, withdrawal of the patient by the Investigator or termination of the study by the Sponsor.

The study population consist of patients with mCRPC, BC, NSCLC or other solid tumors who have failed at least one line of prior treatment and for whom, according to the Investigator, are eligible for low-dose EBRT for at least one symptomatic or minimally symptomatic lesion (for the prevention of symptoms).

The dose levels of EBRT will be either:

- 8 Gray (Gy) as a single fraction, or
- 20/25 Gy as 5 fractions given over 5 to 10 days.

The first EBRT dose fraction must be administered on Day 2 of Cycle 1 and the remaining dose fractions will be given between Day 3 and Day 11. The choice of one of the EBRT dose/fractions stated above will be at the discretion of the Investigator and will be determined by the clinical requirements of the patient. EBRT will be administered according to the institutional protocol.

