4.1.1 Part 1 (Dose Escalation)

Approximately 30 patients with any solid tumor who require low-dose EBRT will be enrolled sequentially to the four planned NOX66 dose groups (Dose Cohort 1: 800 mg [3 to 6 patients]; Dose Cohort 2: 1200 mg; Dose Cohort 3: 1600 mg; Dose Cohort 4: 2400 mg [3 to 8 patients in each of Dose Cohorts 2 to 4]; total daily dose administered twice a day [BID]). At least 2 patients enrolled in Dose Cohorts 2 to 4 must have mCRPC.

The proposed dose regimen for Part 1 is given in Table 4-1. No intra-subject dose escalation is allowed.

	Dose Cohort					
	1	2	3	4		
Total daily dose	800 mg	1200 mg	1600 mg	2400 mg		
Dosing regimen	400 mg BID	600 mg BID	800 mg BID	1200 mg BID		
Number of suppositories per day	$2 \times 400 \text{ mg}$	2 × 600 mg	$4 \times 400 \text{ mg}$	4 × 600 mg		

Table 4-1Proposed Doses for NOX66 (Part 1)

BID = twice daily

All patients will be closely monitored for any dose-limiting toxicities (DLTs) up to Day 21 of Cycle 1.

Dose escalation will be based on an adapted "3+3" design, where dose cohorts will be expanded for up to 6 patients (Dose Cohort 1) in the event of DLT or up to 8 patients (Dose Cohorts 2 to 4) to allow for robust estimation of PK parameters after being deemed "safe" based on the traditional "3+3" design.

At each dose level, 3 patients will initially be treated with NOX66.

- If none of the first 3 patients enrolled in Cohort 1 experience a DLT during the first treatment cycle, the dose will be escalated to the next level.
- If none of the first 3 patients experience a DLT during the first treatment cycle of Cohorts 2 to 4, then the dose level will be deemed "safe" and up to 5 additional patients will be enrolled to the current dose level for estimation of PK parameters. At the same time (with the exception of Cohort 4), the next dose level will be initiated and the first 3 patients will be enrolled to the escalated dose.
- If 1/3 patients experience a DLT, an additional 3 patients will be enrolled. If 1/6 patients experience a DLT then this dose level will be deemed "safe" and, for Cohorts 2 to 4, 2 more patients may be enrolled for estimation of PK parameters. At the same time, the next dose level will be initiated and the first 3 patients will be enrolled to the escalated dose.
- If > 1/3 or > 1/6 patients experience a DLT, then dose escalation will be halted, and the previous dose will be declared as the MTD.

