If the 1200 mg dose is not tolerable (i.e., 2 or more patients with DLTs), an additional 3 patients will be enrolled in the 800 mg dose cohort in order to declare 800 mg as the MTD (if no more than 1/6 patients experience a DLT).

If no DLT is observed at 2400 mg (Dose Cohort 4), dose escalation will be stopped. The proposed highest dose level (2400 mg) will be declared the RP2D.

There will be a temporary halt for enrollment after the first 3 patients are enrolled in each cohort until the SSC clears that the dose level is safe to continue the dose escalation. During the SSC meeting for NOX66 dose escalation decision, the safety and tolerability of both EBRT doses (8 Gy and 20/25 Gy) will also be evaluated. For details on DLT evaluation, see Section 7.1.2.2.

DLT monitoring will be applicable for all patients enrolled in each cohort, including patients enrolled for the purpose of PK analysis; as well as the decision rule for the additional PK patients (i.e., stopping dose escalation).

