In the previous trial, the total duration of NOX66 treatment was up to 16 days and low-dose EBRT of 20 Gy was given in 5 fractionated doses over 5 to 7 days. NOX66 will be administered in this planned study on a 21-day cycle basis (14 days on treatment followed by 7 days off treatment) during Cycle 1, and on a 14-day cycle basis (7 days on treatment followed by 7 days off treatment) from Cycle 2 onwards. NOX66 will be administered until disease progression, unacceptable toxicity, withdrawal of consent, start of a new anticancer therapy, withdrawal of the patient by the Investigator or termination of the study by the Sponsor.

The timings of safety and PK assessments in the study have been designed on the basis of non-clinical and clinical findings. These data will be important to evaluate exposure-response relationships for efficacy and safety in mCRPC and other tumor types.

As part of the clinical drug development program for NOX66, the Sponsor plans to include investigations into PD biomarker profiles and their relation to study drug effect at the intended dosage. These biomarkers will be derived from blood samples taken during the study. There are many potential benefits to this biomarker research, including the possibility to identify patients most likely to benefit from treatment, explain outliers and non-responders or explain adverse reactions related to study drug exposure. This research may result in an understanding of the impact of variation between individuals and how it can be utilized to bring better drug products to the clinic.

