6.1.1 Radiotherapy

The choice of dose/fraction as stated below is Investigator's discretion based on patient's need. Sites will need to follow institutional practice and the guidance provided in Appendix 10 (Section 10.10) for low-dose EBRT administration.

The study population consist of patients with mCRPC, BC, NSCLC or other solid tumors who have failed at least one line of prior treatment and for whom, according to the Investigator, are eligible for low-dose EBRT for at least one symptomatic or minimally symptomatic lesion (for the prevention of symptoms).

The dose levels of EBRT will be either:

- 8 Gy as a single fraction, or
- 20/25 Gy as 5 fractions given over 5 to 10 days.

The first EBRT dose fraction must be on Day 2 of Cycle 1 and the remaining dose fractions will be given between Day 3 and Day 11. The choice of one of the EBRT dose/fractions as stated above will be at the discretion of the Investigator and will be determined by the clinical requirements of the patient. A maximum of 2 sites can be irradiated concurrently in conjunction with NOX66 during Cycle 1. EBRT will be administered according to the institutional protocol.

Additional EBRT at the dose levels/fractions stated above may be given during the study. However, should additional EBRT be considered necessary during the study (Cycle 2 onwards), the Investigator should communicate this to the Medical Monitor for team acknowledgment since extra doses could impact study results.

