- The review of safety and tolerability of both doses of EBRT (8 Gy and 20/25 Gy administered as 1 or 5 fractionated doses).
- All recommendations regarding the replacement of any excluded or withdrawn patients on study, if necessary.*
- * Any patient initiated on treatment in error (i.e., because he or she failed to meet inclusion and/or exclusion criteria) but meeting the criteria of an evaluable patient, will be reviewed on a case-by-case basis by the SSC to determine if the patient should be included or excluded in the recommendation for dose escalation.

See Section 7.1.2.2 for details on DLT assessment.

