Normal Tissue Constraints

In the context of this study, it is a requirement that the radiation oncologist will follow the QUANTEC Guidelines for normal tissue constraints when administering low-dose EBRT (20 Gy in 5 fractions or 8 Gy in 1 fraction) to metastatic lesions⁷. For 25 Gy in 5 fractions, the dosing guidance from the AAPM Task Force Group 101 has to be followed². This study will be excluding all patients who have central nervous system involvement; therefore, the CNS tissue tolerances, with the exception of spinal cord exposure, will not be included in the guidance on normal tissue dose constraints as set out below. These constraints are for EBRT at low dose and for standard fractionation.

Tissue / Organ	Tissue radiation dose constraints (maximum radiation dose)
Spinal cord	23 Gy
Retina	< 50 Gy
Cochlea	\leq 45 Gy
Single parotid gland sparing	< 20 Gy
Irradiation to 2 parotid glands	< 25 Gy (spread across 2 glands)
Mandible	\leq 70 Gy
Pharyngeal constrictors	< 50 Gy
Larynx	< 44 Gy
Brachial plexus	< 60 Gy
Lung	20 Gy
Oesophagus	< 34 Gy
Heart	< 26 Gy
Liver	\leq 28 Gy
Kidney	< 18 Gy per kidney
Stomach	< 50Gy
Small bowel (irradiation to less than one-third)	50 Gy
Rectum	< 27 Gy
Skin	40 Gy
Bladder	< 65 Gy
Femoral head	< 52 Gy

Equipment

Radiation delivery equipment needs to have undergone appropriate dosimetry calibration using an acceptable phantom to ensure that the correct treatment beam energies are being generated, correct alignment between on-board imaging and treatment isocenter, and accurate motion of the treatment couch. This calibration needs to be performed at a minimum of once every 3-4 years to ensure acceptable quality control as per treatment site SOPs.

Treatment Dose Interruptions

Treatment dose interruption for the single fraction Gy regimen is not applicable.

For a patient who will be receiving 20/25 Gy over 5 fractions, dose interruption must occur if a patient experiences a Grade 3 or higher adverse reaction in any organ/tissue that is due to the radiation therapy. The fractionated therapy can only resume once the adverse reaction has recovered or stabilized back to Grade 2 or less.

Patients with tumors involving the central nervous system are excluded from this study. It is anticipated that over 50% of patients recruited into this study will require symptomatic low-dose EBRT to bony metastases, with involvement of other soft tissue organ lesions for the rest of the patients.

References

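### EBRT safety is to be judged with 20 Gy and 25 Gy as one group, and nothing assures that the combination RP2D rests on any patient given 25 Gy (or 8 Gy)

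*Combined protocol and SAP*

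**What the plan says.** Three EBRT regimens are allowed: 8 Gy in 1 fraction, 20 Gy in 5 and 25 Gy in 5 (Sections 4.1 and 6.1.1, Appendix 10). On allocation, Section 4.1 says: "The choice of one of the EBRT dose/fractions stated above will be at the discretion of the Investigator".

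The safety evaluation counts two groups. At the escalation meetings, "the safety and tolerability of both EBRT doses (8 Gy and 20/25 Gy) will also be evaluated" (Section 4.1.1). The SSC's duties include "The review of safety and tolerability of both doses of EBRT (8 Gy and 20/25 Gy administered as 1 or 5 fractionated doses" (Section 7.1.2.1). The secondary objective in Table 3-1 and the title of Section 9.4.7.1 likewise speak of both doses. For the tables, Section 9.4.7.1 states: "Safety profiles will be summarized by NOX66 dose cohort and separately by EBRT dose cohort (Part 1". The EBRT cohorts in that sentence are not defined there.

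Appendix 10 separates 25 Gy in three respects:
- **Normal-tissue guidance.** "For 25 Gy in 5 fractions, the dosing guidance from the AAPM Task Force Group 101 has to be followed", while QUANTEC applies to 20 Gy in 5 and 8 Gy in 1.
- **Simulation.** 4D simulation is mandatory for certain lesions near the diaphragm at 25 Gy and discretionary otherwise.
- **Image guidance.** Instructions are given specifically for 25 Gy.

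The Part 1 objective is the MTD and RP2D of NOX66 combined with low-dose EBRT (Table 3-1). DLTs include events attributed to NOX66 together with EBRT (Section 7.1.2.2). The clearance rule in Section 4.1.1 begins "If none of the first 3 patients experience a DLT during the first treatment cycle of Cohorts 2 to 4" and makes no reference to the EBRT regimen. Of the earlier trial, Section 4.2 says that "low-dose EBRT of 20 Gy was given in 5 fractionated doses over 5 to 7 days".

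**The concern.** The RP2D is a statement about a combination, yet one component varies at the Investigator's choice and two of its three levels are reported as one. If tolerability with NOX66 differs between 20 Gy and 25 Gy, a combined 20/25 Gy row averages the difference away. Separately, a NOX66 dose can be cleared by patients none of whom received a given regimen. All regimens may nevertheless be used at the RP2D in Part 2 (Section 4.1.2). A reader of the final report could take the RP2D as supported for every permitted regimen when the deciding patients covered only some of them.

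**Working it through.** **The plan's own figure.** The Part 1 maximum is 6 (Cohort 1) + 3 × 8 (Cohorts 2 to 4) = 30, which matches Section 9.2. The plan gives no number per EBRT regimen and, being descriptive (Section 9.1), no power or alpha.

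**Is any condition placed on regimen?** Section 4.1.1 clears a dose at 0/3 or 1/6 DLTs without one. Section 7.1.2.2 defines evaluability by DLT status, NOX66 intake and completed safety evaluations, and asks for at least 3 evaluable patients. The only composition rule is a minimum of mCRPC patients. The answer is no.

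**Do the planned outputs recover the split?** Section 9.4.6.1 summarizes DLTs by dose cohort and lists description, severity and relationship to study drug, which Section 2 defines as NOX66. Section 9.4.5 lists the date and time of each EBRT dose. Fraction dates can separate 8 Gy (one fraction) from the other two regimens. They cannot separate 20 Gy from 25 Gy, since both use five.

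**Chance that a regimen is absent.** Let q be the share of patients on 25 Gy, with patients treated as independent. The documents do not give q, so 10% to 50% is assumed. P(none among n) = (1 − q)^n. For example, at q = 0.20 and n = 3, 0.80³ = 0.512. Three patients are the first escalation decision, six are the base of the RP2D definition, and eight are the largest cohort.

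| q | n = 3 | n = 6 | n = 8 |
|---|---|---|---|
| 0.10 | 72.9% | 53.1% | 43.0% |
| 0.20 | 51.2% | 26.2% | 16.8% |
| 1/3 | 29.6% | 8.8% | 3.9% |
| 0.50 | 12.5% | 1.6% | 0.4% |

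The same table applies to 8 Gy if q is read as its share. If the three regimens were equally common, the chance that at least one is missing is 3(2/3)^n − 3(1/3)^n: 77.8% for 3 patients, 25.9% for 6 and 11.7% for 8.

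**Part 2.** It enrols 40 + 24 = 64 to 40 + 30 = 70 patients at one NOX66 dose. At q = 0.10, P(no 25 Gy patient among 64) = 0.90^64 ≈ 0.1%.

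**What small counts can show.** With 0 DLTs among n patients on a regimen, the exact two-sided 95% upper limit is 1 − 0.025^(1/n): 70.8% for n = 3, 45.9% for n = 6 and 36.9% for n = 8.

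**The case against.** The other side has several sound points.

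- **The pooling is inferred.** Section 9.4.7.1 does not define its EBRT cohorts, and Section 9.4 defers detail to the SAP. The inference is strong because the other safety text groups 20/25 Gy, and nothing in the text reviewed splits them.
- **Appendix 10 also treats 20/25 Gy together.** Target coverage, hotspot limits and the interruption rule are common to both. The extra requirements at 25 Gy are safeguards. A reader might infer that the protocol declares 25 Gy a different risk, but it does not say so.
- **The data are not hidden.** The SSC reviews all safety data to Day 21, and Investigators from the enrolling sites are members (Section 7.1.2.1). DLT monitoring and the decision rule continue for the added PK patients (Section 4.1.1). Part 2 will very probably include 25 Gy. A reader might infer that the trial is unable to inform on 25 Gy, or that a 25 Gy toxicity would go unseen; neither follows. The supported statement is that coverage is not assured and the planned grouping does not display it.
- **Two irradiated sites.** Section 6.1.1 says "A maximum of 2 sites can be irradiated concurrently in conjunction with NOX66 during Cycle 1". A reader might infer that one patient can then fall in both EBRT groups. The same section speaks of choosing one regimen, and no section describes mixed regimens in Cycle 1. The documented route to mixed exposure is an additional course (Sections 4.1, 6.1.1 and 6.6.1).
- **Earlier experience.** Section 4.2 describes 20 Gy. It does not say that no other regimen was used, and it refers to the Investigator's Brochure for details.
- **Little inferential yield.** Three regimens by four NOX66 doses make 12 cells for at most 30 patients. At a 20% share, about 0.20 × 30 = 6 patients receive 25 Gy, or 1.5 per NOX66 dose. This stands, but it argues for showing the counts: the upper limits above are what a reader needs to see.

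**Conclusion.** The point holds as a gap in reporting and in the scope of the conclusion. EBRT safety is to be evaluated in two groups although three regimens are allowed and the protocol plans 25 Gy under separate requirements. The RP2D in combination with EBRT is not assured to rest on any patient given 25 Gy, or 8 Gy. At an assumed 20% share (range 10% to 50%), the chance of no 25 Gy patient at a NOX66 dose is 51% (73% to 13%) among the first 3, 26% (53% to 2%) among 6 and 17% (43% to 0.4%) among 8. These figures rest on the assumed share and on independence between patients. Part 2 would probably add 25 Gy exposure, but it has no DLT-based decisions and, on the same grouping, would report that exposure together with 20 Gy. The documents do not show that toxicity with NOX66 differs between 20 Gy and 25 Gy, and this point does not claim that it does.

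**What to change.** 1. In Section 9.4.7.1, define the EBRT strata as 8 Gy in 1 fraction, 20 Gy in 5 and 25 Gy in 5.
2. Report DLTs and TEAEs with denominators by these strata, and add a count table of NOX66 dose by regimen for Part 1.
3. Add the EBRT regimen to the DLT listing (Section 9.4.6.1) and to the SSC review (Section 7.1.2.1).
4. Classify each patient by the Cycle 1 regimen and flag any later additional course.
5. Beside the RP2D, state how many DLT-evaluable patients received each regimen at that dose, and limit the tolerability conclusion to regimens with data.

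Two statements in Appendix 10 should be reconciled first, because they bear on the strata. Its simulation text gives 20 Gy in 4 fractions where the rest of the protocol has 5. Its imaging text for 25 Gy is optional in one sentence and mandatory in the next.

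The cost is table programming, one extra listing column and one added SSC display, with no further patients or procedures and no change to any dose or clinical rule. The downside is small cells and a narrower RP2D statement.
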